#### Secondary objectives

1. Determine if MRI imaging is superior to CT imaging in delineating a high risk target volume.
2. Identify clinical and tumor characteristics of patients in whom CT or MRI can improve dosimetric tumor coverage and normal tissue sparing.
3. Evaluate the feasibility of MRI-based treatment planning utilizing the shielded MD Anderson adaptive applicator.
4. Compare resource utilization for MRI and CT based treatment planning as compared to standard film based planning techniques.

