It is important to clarify the magnitude of potential benefit from these new approaches because utilization of 3D image-based treatment planning is substantially more expensive than standard planning; one study reported increased costs of 10-15% to setup 3D image based gynecologic brachytherapy. MRI in particular, despite its potential benefits, is expensive, logically difficult and is not as widely available for radiation oncology treatment planning as CT imaging. It also requires the use of specially-designed MRI-compatible applicators. As a result, Viswanathan and colleagues suggested a standardized approach to CT-based contouring. When the authors compared CT with MRI, they found that CT was adequate for analysis of the doses to organs at risk, but that CT-based standardized contours tended to overestimate tumor width, leading to significant differences in target coverage. While this study is the only published series comparing CT to MRI, it included only 10 patients with a single radiation oncologist responsible for the contouring. Additionally, the CT quality was poor (with 4 mm slice thickness) compared to current standards (typically 1-2 mm slice thickness). To date, there are no studies evaluating the role of modern CT scanning in an adequate number of patients to determine if there is a select group in which CT may be equivalent to MRI in delineating a target volume.

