#### Dosimetric Contouring Study

As part of the lab based portion of this protocol, the MRI and CT images will be uploaded into our brachytherapy treatment planning software, Oncentra. After reviewing the patient's initial diagnostic imaging and physical examination at the time of diagnosis and the time of implant the radiation oncologist involved in the procedure and one additional radiation oncologist will contour a HR-CTV based on the GEC-ESTRO guidelines (Appendix E) on the CT followed by the MRI. One of the primary investigators will also contour a HR-CTV as well as critical structures (rectum, bladder, sigmoid colon) on both the MRI and CT scan. The 2D plan will then be registered on the MRI and CT within the treatment planning software. Based on the primary investigators approved contours several additional plans will be created for purpose of comparison (See Table 1).

The contours devised by all three physicians on MRI and CT will also be compared to determine the interobserver variability for each specific imaging modality. Contours will be imported into Computerized Environment for Radiation Research (CERR), an open-source MATLAB (TheMathWorks, natick, MA) - based radiation therapy planning analysis tool. The "apparant agreement" method will be used to calculate the apparent volume overlap such that a volume - agreement cumulative histogram can be generated.

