#### Dosimetric Treatment Planning Study

The first plan will be a CT based plan and will be optimized to improve the HR-CTV D90 (dose received by 90% of the target volume) to as close to 85 Gy as possible without exceeding the known tolerance dose to rectum and bladder (D2cc of rectum  $\leq$  70 Gy and D2cc of bladder  $\leq$  90 Gy). The second plan will be optimized the same as the first but with the HR-CTV, rectum, and bladder delineated on MRI instead of CT.

Table 1

Plan	Description
1) 2D Plan	This will be based on the standard loadings recommended by the physician after performing physical exam at time of implant and review of orthogonal films delineating applicator placement. The initial diagnostic imaging will be reviewed and help to inform this plan and adjustments will be made based on point doses.
2) 2D Plan informed by 3D images at time	This will be based on the standard loadings

of implant.	recommended by the physician after performing physical exam at time of implant and review of orthogonal films delineating applicator placement. The initial diagnostic imaging as well as the MRI and CT scan at the time of implant will be reviewed and help to inform this plan. The patient will be treated with this plan according to standard practice.
3) ICBT CT based optimized plan	This plan will start with the above described 2D plan and will be optimized to target the CT based HR-CTV (also informed by initial diagnostic imaging) with the same objectives as the GEC-ESTRO MRI guidelines.
4) GEC-ESTRO MRI based optimized plan	This plan will start with the above described 2D plan and will be optimized according to GEC-ESTRO guidelines taking into account the patient's initial diagnostic imaging as well as MRI scan with the applicator in place.

Each of the three treatment plans will be registered on the MRI, and the MRI contours will be used as the gold standard such that each treatment plan will be evaluated for its coverage of the HR-CTV and ability to meet constraints for the adjacent organs at risk. For each of the three treatment plans, we will evaluate the D90, D100, V100, V150, V200, for the HR-CTV and IR-CTV as well as the D0.1, 1, 2 cc for bladder, sigmoid, and rectum (see Table 2). Conformality index (CI=V100%/VCTV) and dose homogeneity index (DHI= (V100%-V150%)/V100%) will be calculated for HR-CTV.

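### Secondary objective 1 claims a test of MRI superiority in delineation, but the plan measures only reader agreement within each modality, by an overlap index whose dependence on contour size is left undefined

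*Combined protocol and SAP*

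**What the plan says.** - **Section 1.0, Secondary objectives:** objective 1 is to "Determine if MRI imaging is superior to CT imaging in delineating a high risk target volume".
- **Section 5.0, Dosimetric Contouring Study:** three physicians contour the HR-CTV on both scans. Their contours are "compared to determine the interobserver variability for each specific imaging modality". The agreement "method will be used to calculate the apparent volume overlap such that a volume - agreement cumulative histogram can be generated". The section does not say whether overlap is in cc or a fraction. It gives no summary statistic, no CT-MRI contrast and no test. Two of the three readers contour "on the CT followed by the MRI"; no order is stated for the third.
- **Section 5.0, Dosimetric Treatment Planning Study:** for scoring the treatment plans, "the MRI contours will be used as the gold standard".
- **Section 6.0, Analysis and Secondary Endpoint:** these cover dose parameters, planning and imaging time, and fees. Neither contains a delineation endpoint.
- **Section 2.0, Image Guided Brachytherapy:** in the one earlier CT-MRI series, "CT-based standardized contours tended to overestimate tumor width, leading to significant differences in target coverage". The protocol adds that "it included only 10 patients with a single radiation oncologist responsible for the contouring" and that its 4 mm CT slices were poor. The same section says tumor is hard to tell from normal cervix on CT.

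**The concern.** A superiority claim about delineation needs either a reference that does not come from MRI or a narrower question that the data can answer. The plan has neither. Three readers can agree closely on a contour that is too wide, so good agreement does not show that a modality finds the target.

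The agreement measure adds a second difficulty. If readers differ by the same number of millimetres at the edge, a larger contour leaves a larger shared volume. The background expects CT contours to be wider, so CT and MRI may differ on overlap for reasons unrelated to reader disagreement. With the index undefined, the ranking of the two modalities could turn on a choice made after the contours are seen. At stake is the study's answer to its first secondary objective.

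**Working it through.** **1. The plan's own figure.** None is given for objective 1 or for the contour comparison. The primary power statement does reproduce: 273.75/303.69 = 0.901, and a paired t-test with n = 30 and two-sided alpha 0.0056 has 96.6% power against the stated 96%. It concerns HR-CTV D90 and has no bearing on delineation.

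**2. Can any planned analysis answer objective 1?**
- *Reader agreement:* uses no reference, so it measures precision only.
- *Dose comparison:* the MRI plan is optimised to MRI contours and scored on them. The CT plan is optimised to CT contours and scored on MRI contours. Any CT-MRI difference counts as CT error, whichever contour was nearer the truth.
- *Time and fees:* not about delineation.

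**3. How far does overlap depend on size?** All sizes and SDs here are assumptions; the documents give none. Take an MRI target with semi-axes 20, 20, 20 mm, a CT target 25% wider in one axis (25, 20, 20 mm), and three readers with independent N(0, 3 mm) error on each semi-axis.

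Hand check: the mean of the smallest of three normal draws lies 3/(2√π) = 0.846 SD below the centre. The smallest semi-axes average 20 − 0.846 × 3 = 17.46 mm and 25 − 2.54 = 22.46 mm. The ellipsoid with the smallest axes lies inside the common volume, so it gives a lower bound:
- MRI: (4π/3) × 17.46³ = 22.3 cc
- CT: (4π/3) × 22.46 × 17.46² = 28.7 cc
- Ratio: 22.46/17.46 = 1.29

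Simulation of the actual intersection and union, in four separate runs:

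| Run | Common volume, MRI → CT (cc) | Change | Common/union, MRI → CT | Change |
|---|---|---|---|---|
| 1 | 24.0 → 31.0 | +29% | 0.556 → 0.589 | +0.033 |
| 2 | 24.4 → 30.6 | +25% | 0.560 → 0.584 | +0.024 |
| 3 | 24.0 → 30.8 | +28% | 0.557 → 0.585 | +0.028 |
| 4 | 24.4 → 30.7 | +26% | 0.565 → 0.579 | +0.014 |

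In run 2 the standard error of a mean fraction was about 0.007, so a difference has a standard error of about 0.007 × √2 = 0.010. The gain in the fraction is close to simulation noise.

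**4. What if CT readers disagree more?**
- *Absolute volume:* the wider CT target at 3 mm SD gave 30.9 cc against 27.1 cc for MRI at 2 mm SD. CT ranks higher with 3/2 = 1.5 times the reader error.
- *Fraction:* in run 3, with CT at 3.3 mm SD (10% more), the fraction was 0.557, equal to MRI at 3 mm. At 3.5 mm it was 0.539 and at 4 mm 0.496, both below MRI.

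A different model (semi-axes 17.5, 15, 17.5 mm, with error in position as well as size) shows the same split. CT 30% wider at 3 mm SD, against MRI at 2 mm SD, gave 12.6 against 12.2 cc, but fractions of 0.33 against 0.46. The two readings of overlap rank the modalities differently.

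**5. Does a boundary measure avoid this?** Mean pairwise radial distance between readers, a stand-in for surface distance, was 2.64 mm for the base target, 2.66 mm for the wider one and 2.59 mm for a target enlarged in every axis. It rose from about 1.7 mm at 2 mm SD to about 2.6 mm at 3 mm SD. It follows reader error and is nearly flat with size.

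**The case against.** The strongest reply has four parts.

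- **The agreement analysis is not circular.** A reader might infer that the gold-standard wording decides the contour comparison in advance. It does not: that wording governs plan evaluation, and the agreement analysis uses no MRI reference. This stands. Accuracy is untestable there because no reference independent of MRI exists.
- **A bias towards CT is not established.** A reader might infer that the measure favours CT. That needs overlap in absolute volume, which the documents do not state, and equal reader error, which the protocol's remark on poor tumor visibility on CT makes doubtful. With a fraction, slightly worse CT reading removes the effect. This stands too.
- **The evidence for larger CT contours is thin.** It concerns width only, gives no size, and comes from 10 patients, one contouring physician and 4 mm slices; this study uses 2 mm. Enlargement in every axis has no basis in the documents.
- **The plan never says overlap will decide objective 1** or support a finding that CT equals MRI. True, but then objective 1 has no analysis at all.

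It can also be said that surface distance measures precision too, and that a stated, normalised overlap index would remove most of the size effect. Both are correct. The first is why the objective must be reworded as well as the measure changed.

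**Conclusion.** The concern holds in two parts of unequal strength.

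**Firm, and free of simulation assumptions:** objective 1 claims superiority in delineation, and nothing in the plan can show it. Reader agreement is precision, the analysis sections contain no delineation endpoint or CT-MRI contour contrast, and the dose comparison treats MRI as truth.

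**Conditional:** the overlap measure depends on contour size. For a contour 25% wider in one axis with equal edge error, the effect is roughly 25 to 29% in absolute volume, enough to rank CT above MRI when CT readers disagree more. As a fraction it is about 0.01 to 0.03, cancelled by about 10% more CT reader error. These figures rest on assumed sizes, ellipsoid shapes and SDs. The plan does not say which form applies, so neither a net bias nor its direction can be claimed.

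The objective is secondary and patient treatment is unaffected. The change is worth making because it is cheap and settles the index before the contours are compared.

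**What to change.** - Reword secondary objective 1 to: *determine whether HR-CTV delineation is less variable between observers on MRI than on CT*.
- In the Dosimetric Contouring Study, define the CT-MRI comparison as a within-patient paired contrast, with a confidence interval, of mean pairwise surface distance (mm) among the three readers.
- Report contour volume and transverse width beside it, so that a size difference between modalities is visible.
- Keep the apparent-agreement histogram as descriptive.

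The cost is the superiority wording, some text in the objectives and analysis sections, and one more calculation on contours already due to be imported into CERR. No new readers, scans or contours are needed.

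One limit remains. Two readers contour CT before MRI, so for them modality is confounded with reading order. Surface distance does not cure that, and the report should say so.

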#### Dosimetric Treatment Planning Study

The first plan will be a CT based plan and will be optimized to improve the HR-CTV D90 (dose received by 90% of the target volume) to as close to 85 Gy as possible without exceeding the known tolerance dose to rectum and bladder (D2cc of rectum  $\leq$  70 Gy and D2cc of bladder  $\leq$  90 Gy). The second plan will be optimized the same as the first but with the HR-CTV, rectum, and bladder delineated on MRI instead of CT.

Table 1

Plan	Description
1) 2D Plan	This will be based on the standard loadings recommended by the physician after performing physical exam at time of implant and review of orthogonal films delineating applicator placement. The initial diagnostic imaging will be reviewed and help to inform this plan and adjustments will be made based on point doses.
2) 2D Plan informed by 3D images at time	This will be based on the standard loadings

of implant.	recommended by the physician after performing physical exam at time of implant and review of orthogonal films delineating applicator placement. The initial diagnostic imaging as well as the MRI and CT scan at the time of implant will be reviewed and help to inform this plan. The patient will be treated with this plan according to standard practice.
3) ICBT CT based optimized plan	This plan will start with the above described 2D plan and will be optimized to target the CT based HR-CTV (also informed by initial diagnostic imaging) with the same objectives as the GEC-ESTRO MRI guidelines.
4) GEC-ESTRO MRI based optimized plan	This plan will start with the above described 2D plan and will be optimized according to GEC-ESTRO guidelines taking into account the patient's initial diagnostic imaging as well as MRI scan with the applicator in place.

Each of the three treatment plans will be registered on the MRI, and the MRI contours will be used as the gold standard such that each treatment plan will be evaluated for its coverage of the HR-CTV and ability to meet constraints for the adjacent organs at risk. For each of the three treatment plans, we will evaluate the D90, D100, V100, V150, V200, for the HR-CTV and IR-CTV as well as the D0.1, 1, 2 cc for bladder, sigmoid, and rectum (see Table 2). Conformality index (CI=V100%/VCTV) and dose homogeneity index (DHI= (V100%-V150%)/V100%) will be calculated for HR-CTV.

Table 2 Using the contours created on MRI (HR-CTV, IR-CTV, Rectum, Bladder, Sigmoid) the following parameters will be evaluated for each of the three treatment plans.

HR-CTV*	IR-CTV	Rectum	Bladder	Sigmoid
D90**	D90	D 0.1cc	D 0.1cc	D 0.1cc
D100	D100	D 1 cc	D 1 cc	D 1 cc
V100	V100	D 2 cc	D 2 cc	D 2 cc
V150	V150			
V200	V200			

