### Contouring and Treatment Planning

As is standard, our dosimetrists will develop a 2D plan according to the loadings recommended by the physician based on the physical examination, initial diagnostic imaging ,and orthogonal films. As is routine the treating physician will then evaluate the 2D plan looking at doses to specific points (rectal and bladder) delineated on the 2D imaging and make adjustments as they see fit. Following acquisition of both MRI and CT and finalizing of the 2D treatment plan, images will be reviewed by the treating physician before treatment to rule out any possible rare major deviations in applicator placement such as uterine perforation. The 3D imaging will also be used to inform the physician prescribing the dose of the location and size of any residual disease and

location of critical organs such that they may make subtle adjustments to the 2D treatment plan. Based on this a new plan, 2D plan informed by 3D imaging, will be created, and the patient will be treated with this plan.

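### Only the MRI plan is, on the natural reading, scored on the same investigator's contours it was optimised to; D90 is not checked on the other two readers' MRI targets, and no CT-first order is stated for that investigator

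*Combined protocol and SAP*

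**What the plan says.** All references are to the combined protocol and SAP.

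**Who contours.** Under Dosimetric Contouring Study (section 5.0), two oncologists draw an HR-CTV: the one who took part in the implant, and a second. The instruction for this pair reads: "one additional radiation oncologist will contour a HR-CTV based on the GEC-ESTRO guidelines (Appendix E) on the CT followed by the MRI". A primary investigator "will also contour a HR-CTV as well as critical structures (rectum, bladder, sigmoid colon) on both the MRI and CT scan"; no order is given for this reader.

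**What the plans are built on.** The same section says: "Based on the primary investigators approved contours several additional plans will be created for purpose of comparison". The Dosimetric Treatment Planning Study describes the CT-based plan first (plan 3 in Table 1) and then the MRI-based plan (plan 4): "The second plan will be optimized the same as the first but with the HR-CTV, rectum, and bladder delineated on MRI instead of CT".

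**What the plans are scored on.** "Each of the three treatment plans will be registered on the MRI, and the MRI contours will be used as the gold standard". The Table 2 caption repeats this: "Using the contours created on MRI (HR-CTV, IR-CTV, Rectum, Bladder, Sigmoid) the following parameters will be evaluated for each of the three treatment plans". Neither place says whose MRI contours are meant. Both speak of three plans, while Table 1 lists four.

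**What the other contours are for.** The three physicians' contours "will also be compared to determine the interobserver variability for each specific imaging modality", by a volume-overlap method. Sections 5.0 and 6.0 plan no dose calculation on the other two oncologists' HR-CTVs.

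**Who sees the implant MRI before treatment.** Under Contouring and Treatment Planning: "The 3D imaging will also be used to inform the physician prescribing the dose of the location and size of any residual disease".

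**The concern.** HR-CTV D90 is part of the primary endpoint and carries the 20% improvement target in section 6.0, Sample Size. If one reader's MRI contour set is both the target of plan 4 and the yardstick for every plan, then part of any D90 gain may belong to that reader's drawing and not to MRI guidance as such. Nothing planned would show how much. The Background criticises the earlier CT-versus-MRI comparison partly because a single oncologist did the contouring. This study collects three readers' targets but, on the natural reading, rests its dosimetric result on one.

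The order of contouring raises a second question. Plan 3 is meant to show what CT-based planning achieves. If the investigator sees the implant MRI before drawing on CT, the CT contour carries MRI information and plan 3 no longer represents CT-only planning.

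Plans 3 and 4 are for comparison only (section 3.0), so this bears on the study's conclusion and not on any patient's treatment.

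**Working it through.** **1. Target and yardstick, plan by plan** (Table 1, Dosimetric Contouring Study, Dosimetric Treatment Planning Study)

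| Plan | Shaped by | Scored on | Same contours? |
|---|---|---|---|
| 1. 2D | Standard loadings, examination, films, diagnostic imaging, point doses | MRI contours | No |
| 2. 2D informed by 3D | As plan 1, plus review of implant MRI and CT | MRI contours | No |
| 3. CT optimised | Investigator's CT contours | MRI contours | No |
| 4. MRI optimised | Investigator's MRI contours | MRI contours | Yes, if the scoring reader is the investigator |

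The last cell is an inference. For bladder and rectum it is strong, because only the investigator is stated to contour organs. For HR-CTV three MRI versions exist and the scoring one is not named. The investigator's is the natural choice, because it belongs to the only full set described.

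**2. Direction.** The shared target and yardstick can favour plan 4, but this does not work one way only. Plan 4 does not maximise D90 freely: it aims for 85 Gy within rectum and bladder limits. An organ drawn too large can make a limit bind early and lower plan 4's D90. An HR-CTV drawn too large can do the same when those limits bind. An HR-CTV drawn too small can raise the scored D90 of plans 1 to 3. Any contour effect common to all plans cancels in the paired difference.

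**3. Size.** The documents give no figure for between-reader variation in D90, so the effect cannot be estimated.

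**4. Contouring order.** The two oncologists are told CT and then MRI. The investigator's sentence names both scans without an order. Appendix E, cited there for the contouring guideline, is not in the text available.

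**5. Precision of the proposed check.** Inputs from Sample Size: SD of the paired MRI-minus-2D difference in D90, 303.69 cGy (4 patients); mean D90 on the 2D plan, 1368.73 cGy; target gain 273.75 cGy; n = 30; two-sided level 0.0056.

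- Plan's own figure: a paired t-test with 29 df and standardised effect 273.75 / 303.69 = 0.901 gives 96.7% power from the noncentral t distribution. The plan states 96%, so its design figure reproduces.
- SE = 303.69 / √30 = 55.45 cGy.
- 95% half-width = 2.045 × 55.45 = 113.4 cGy, or 113.4 / 1368.73 = 8.3% of the 2D mean.
- 95% interval for the SD under normality: 303.69 × √(3 / 9.348) = 172.0 to 303.69 × √(3 / 0.2158) = 1132.3 cGy.
- Half-width over that interval: 64.2 to 422.8 cGy.

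These figures assume that the paired SD on another reader's contour equals the pilot SD. No SD is given for MRI minus CT.

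**The case against.** The strongest case on the other side has four parts.

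- **MRI as reference is a declared and reasoned choice.** The Background says why MRI shows tumour better than CT. Scoring on another reader's target asks about robustness, which supplements the planned primary question. This stands, and it is why the MRI reference and the primary analysis should stay.
- **No bias is demonstrated.** This also stands. A reader might infer that contour error can only hurt the other plans and never plan 4, so that the gain is inflated by construction. The 85 Gy aim and the organ limits rule out so one-sided a statement. A reader might also infer that the primary result would lose significance once the contour effect is removed. The documents do not size that effect, and the only SD comes from 4 patients, so this is unsupported.
- **The same contouring order may be intended for the investigator.** The sentence follows directly on the CT-then-MRI instruction. This stands: it is a gap in the text, not a proven reversal.
- **It is not certain that nobody else contours organs.** Table 2 scores an IR-CTV that no one is assigned to draw, so the list of who contours what is incomplete. The text supports only that the investigator is the one reader stated to contour bladder and rectum.

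A reader might further infer that the MRI reference makes secondary objective 1 (MRI versus CT delineation) circular. No section assigns the dosimetric comparison to that objective, and the contouring study compares readers within each modality without an MRI reference.

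None of this answers the remaining point: the data for a D90 check on two other readers' targets are collected, and no such check is planned.

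**Conclusion.** The concern holds in a limited form. Plan 4 is the only compared plan for which optimisation target and scoring reference coincide, given that the investigator's MRI contours do the scoring. That may favour plan 4 in the D90 comparison, by an amount the documents do not allow one to estimate. The planned overlap analysis is geometric and cannot show whether the D90 gain holds on another reader's target. The unstated contouring order leaves open whether plan 3 represents CT-only planning.

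This is an improvement the study should make. It is not an error in its figures. Confidence is medium, because the identity of the scoring reader is inferred.

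**What to change.** 1. **Scoring.** Keep the MRI reference and the planned primary analysis. State which plans are compared, and that primary scoring uses the investigator's MRI contours. Pre-specify a sensitivity analysis that recomputes HR-CTV D90 for every compared plan on each of the other two oncologists' MRI HR-CTVs separately. Report the paired MRI-minus-2D and MRI-minus-CT differences with 95% intervals beside the primary result, with no significance rule. Report bladder and rectum D2cc with the caveat that only the investigator is stated to contour those organs, so the same check is not available for them.

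2. **Order.** Require the investigator to complete and lock the CT contours before opening the implant MRI. Report CT interobserver agreement with and without the treating oncologist, who may already have seen that MRI when finalising the treated plan.

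**Cost.** Extra dose-volume read-outs on contours already collected and an order rule for one reader; no added reader, scan or patient. The plan-4 gain may look less favourable, and one CT agreement analysis will rest on two observers. The D2cc dependence on one reader remains. Because the intervals will be moderately wide, a smaller gain on another reader's contour would not by itself prove bias.
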